7. RESEARCH QUESTION AND OBJECTIVES

The aim of the study is to contextualise the risk of venous and arterial thromboembolic events associated with COVID-19, during the Omicron period and SARS-CoV-2 vaccination. To do so, the research objectives are:

1. To estimate the background incidence rate of venous and arterial thromboembolic events among the general pre-pandemic population.
2. To estimate the incidence rate of venous and arterial thromboembolic events among patients with COVID-19 within 30-, 60-, and 90- and 180-days during the Omicron period, stratified by prior SARS-CoV-2 vaccination and prior infection status.
3. To estimate the incidence rate of venous and arterial thromboembolic events among patients with SARS-CoV-2 vaccination within 30-, 60-, 90- and 180-days, stratified by prior infection status.
4. To estimate a) the association between clinical risk factors, including prior SARS-CoV-2 vaccination, on the incidence rate of venous and arterial events among people with COVID-19 and b) the impact that thromboembolic events have on worsening severity of COVID-19 during the Omicron period.
5. To estimate incidence rate ratios for venous and arterial thromboembolic events among patients with COVID-19 and different SARS-CoV-2 vaccine doses compared to the background population, using incidence rates estimated in objectives 1 to 3.

Table X: Primary and secondary research questions and objective

A. Primary research question and objective

Objective:	
 1. To estimate the background incidence rate of venous and arterial thromboembolic events among the general pre-pandemic population. 2. To estimate the incidence rate of venous and arterial thromboembolic events among patients with COVID-19 within 30-, 60-, and 90- and 180-days during the Omicron period, stratified by prior SARS-CoV-2 vaccination and prior infection status.
-------------------	---

	Phase II C3-001 – Study Protocol	
	Author(s): [name], [name]	Version: v3.1
	Dissemination level: public	

	
3. To estimate the incidence rate of venous and arterial thromboembolic events among patients with SARS-CoV-2 vaccination within 30-, 60-, 90- and 180-days, stratified by prior infection status.
 
4. To estimate a) the association between clinical risk factors, including prior SARS-CoV-2 vaccination, on the incidence rate of venous and arterial events among patients with COVID-19 and b) the impact that thromboembolic events have on worsening severity of COVID-19 during the Omicron period.
 
5. To estimate incidence rate ratios for venous and arterial thromboembolic events among patients with COVID-19 and different SARS-CoV-2 vaccine doses compared to the background population, using incidence rates estimated in objectives 1 to 3.

Hypothesis:	
Objective 1 – 3 are descriptive incidence rate, not applicable.
 
Objective 4: Some factors/ characteristics are associated with a) the incidence of venous and arterial thromboembolic events among patients with COVID-19 and b) worsening of COVID-19 during the period whenOMICRON was the dominant variant.
 
Objective 5: Being infected with Omicron variant or being vaccinated may be related to changes in the incidence rates of thromboembolic events.

Population (mention key inclusion-exclusion criteria):	
Objective 1: General population cohort for pre-pandemic background rates will have:
 
 • people included in the database as of 1 January 2017 or when they fulfil 365 days of prior history. • follow-up for this cohort will run up to 31 December 2019. 
Objective 2: Persons tested positive for SARS-CoV-2 or with a clinical diagnosis of COVID-19 during the Omicron period will:
 
 • have either a positive test result for SARS-CoV-2 or a clinical diagnosis of COVID-19 on or after 1st December 2021 (with the index date being whichever date comes first if both occur) • have no positive test result for SARS-CoV-2 or clinical diagnosis of COVID-19 within 3 months prior to the index date. 
Objective 3: Persons vaccinated against SARS-CoV2 infection:
 
 • a vaccination record identified by brand (with the index date the date of vaccination record) and not any other record of vaccine in the prior 21 days. The 21 days was based on the

	Phase II C3-001 – Study Protocol	
	Author(s): [name], [name]	Version: v3.1
	Dissemination level: public	

	
shortest dosing schedule for primary vaccination series in the participated databases (SIDIAP in Spain)
 
 whether the vaccination record is 1st, 2nd, 3rd or 4th dose. 
Objective 4: Persons requiring intensive services during a hospitalisation with COVID-19 during the Omicron period will have:
 
 intensive services initiated during a hospitalisation. 
Objective 5: same as objective 1-4

Exposure:	
Objective 1: N/A
 
Objective 2: SARS-CoV-2 infection
 
Objective 3: Vaccination against SARS-CoV2 infection
 
Objective 4: Incidence VTE or ATE, or worsening severity after SARS-CoV2 infection
 
Objective 5: SARS-CoV2 infection and Covid-19 vaccines

Comparator:	
Objective 1 – 3 are descriptive incidence rate, not applicable.
 
Objective 4: No incidence VTE or ATE, or worsening severity after SARS-CoV2 infection
 
Objective 5: background population

Outcome:	
1. Venous thromboembolic events
 
In the primary analysis, venous thromboembolic events will be identified by diagnostic codes for pulmonary embolism or deep vein thrombosis.
 
2. Arterial thromboembolic events
 
In the primary analysis, arterial thromboembolic events will be identified by diagnostic codes for an acute myocardial infarction or acute ischemic stroke.

Time (when follow up begins and ends):	
Objective 1: follow-up will begin on January 1st 2017 or 365 days of prior history and continue up until the first of: outcome of interest, loss to follow-up, death or December 31st 2019.
 
Objective 2: follow-up will begin on their index date and continue up until the first of: outcome of interest, loss to follow-up, death, or either 30-, 60-, 90- or 180-days after the index date (depending upon the follow-up time period of interest).
 
Objective 3: follow-up will begin on their index date and continue up until the first of: outcome of interest, loss to follow-up, death, or

	Phase II C3-001 – Study Protocol	
	Author(s): [name], [name]	Version: v3.1
	Dissemination level: public	

	either 30-, 60-, 90- or 180-days after the index date (depending upon the follow-up time period of interest).
Setting:	Inpatient and outpatient setting using data from the following datasources: IPCI (NL), SIDIAP (Spain), IQVIA Germany (Germany), Estonian Biobank – via Utartu (Estonia) and CPRD GOLD (UK). Inpatient information is only available in SIDIAP.
Main measure of effect:	The incidence of each study outcome will be estimated during 30-, 60-, and 90- and 180-days following the index date for the general pre-pandemic population cohort, the people with COVID-19 cohort, and the vaccinated cohort with 95% confidence intervals. The 90-day cumulative incidence of study outcomes will be estimated. Incidence rate ratios will be calculated.

B. Secondary research question and objective

Outcome:	
For the secondary analysis, we will be looking at the outcomes in the primary analysis separately, with additional outcome events as well. All other contents in the table are the same as the primary.
 
 1. Venous thromboembolic events 
In a secondary analysis pulmonary embolism and deep vein thrombosis will be assessed separately. We will also assess portal vein thrombosis, splanchnic venous thrombosis (SVT) and cerebral venous sinus thrombosis separately.
 2. Arterial thromboembolic events 
In a secondary analysis acute myocardial infarction and acute ischemic stroke will be assessed separately. We also identify stroke in general, for which we will include both ischemic, haemorrhagic and non-specifically recorded stroke.
 3. Cardiovascular events 
Instances of heart failure, cardiac arrhythmia, and angina will be identified. In addition, major cardiovascular events (MACE) will be identified by heart failure, acute myocardial infarction, or stroke, or the occurrence of sudden cardiac death. As a sensitivity analysis, we will require that events were identified by hospitalisation admission or discharge records.

-----------------	--

8. RESEARCH METHODS

	Phase II C3-001 – Study Protocol	
	Author(s): [name], [name]	Version: v3.1
		Dissemination level: public

8.1 Study type and Study Design

STUDY TYPE	STUDY DESIGN	STUDY CLASSIFICATION
Drug/Vaccine Safety Studies	New User Cohorts	Complex (C3)

8.2 Study Setting and Data Sources

The selection of databases for this study was performed based on data reliability and relevance for the proposed research question among those databases onboarded and available within DARWIN EU. The selected databases fulfil the criteria required for the availability of key information on exposures, outcomes, and covariates, while covering different settings and regions of Europe.

Records on Covid-19 infection and vaccination (needed for objectives 2 to 5) will be available in all purposed databases except Estonia Biobank. We have previously published studies showing that these databases can generate reliable evidence on COVID-19 research. [20–22] Specifically, the availability of covid-19 tests results, and linked vaccination records through national/regional immunization program (SPRD, SIDIAP) increased the reliability of the identified study exposures. Inpatient admission and intensive care use (needed for objective 4) will be available in SIDIAP, which provides primary care records with linked hospitalization information.

Table 1. Description of the selected Data Sources.

Country	Name of Database	Justification for Inclusion	Health Care setting (e.g. primary care, specialist care, hospital care)	Type of Data (EHR, claims, registries)	Number of active subjects	Feasibility count of exposure (if relevant)	Feasibility count of disease (if relevant)	Data lock for the last update
Spain	SIDIAP	Complete records on SARS-CoV-2 infection, Covid-19 vaccination, and outcome events of interest; Include inpatient admission information. (objectives 1 to 5)	primary care database + linkage to hospital data	EHR	5.8M	Covid-19: 3865976, AstraZeneca :1152432, Janssen :257806, Pfizer :6548545, Moderna :3371395	VTE as example for all databases. 101966	1/6/2022
The UK	CPRD GOLD	Complete records on SARS-CoV-2 infection, Covid-19 vaccination,	primary care	EHR	3M	Covid-19: 360198, AstraZeneca	219844	07/2022

	Phase II C3-001 – Study Protocol	
	Author(s): [name], [name]	Version: v3.1
	Dissemination level: public	

Country	Name of Database	Justification for Inclusion	Health Care setting (e.g. primary care, specialist care, hospital care)	Type of Data (EHR, claims, registries)	Number of active subjects	Feasibility count of exposure (if relevant)	Feasibility count of disease (if relevant)	Data lock for the last update
		and outcome events of interest (objectives 1 to 5, exclude 4b on worsening covid-19)				:2360815, Janssen :3034, Pfizer :2822947, Moderna :311069		
Germany	IQVIA Germany	Complete records on SARS-CoV-2 infection, Covid-19 vaccination, and outcome events of interest (objectives 1 to 5, exclude 4b on worsening covid-19)	outpatient visits of primary care physicians and a sample of specialists	EHR	8.5M	Covid-19:1723895, AstraZeneca :189261 , Janssen :83771 , Pfizer :2614482 , Moderna :428057	392674	1/9/2022
The Netherlands	IPCI	Complete records on SARS-CoV-2 infection, Covid-19 vaccination, and outcome events of interest (objectives 1 to 5, exclude 4b on worsening covid-19)	Primary care	EHR	1.39M	Covid-19: 941329, AstraZeneca :178192 , Janssen :19645 , Pfizer :1173104 , Moderna :463315	57087	1/12/2022

	Phase II C3-001 – Study Protocol	
	Author(s): [name], [name]	Version: v3.1
	Dissemination level: public	

Country	Name of Database	Justification for Inclusion	Health Care setting (e.g. primary care, specialist care, hospital care)	Type of Data (EHR, claims, registries)	Number of active subjects	Feasibility count of exposure (if relevant)	Feasibility count of disease (if relevant)	Data lock for the last update
Estonian	Estonian Biobank	Geographic representative (objective 1 only)	Biobank	EHR	0.2M	79411 (Covid-19)	25766	31/3/2021

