		Dissemination level: public

We will calculate crude incidence rate ratios (IRRs) for each event with 95% confidence intervals, for the vaccinated and COVID-19 cohorts compared against the background general population cohort. This will be done both overall and stratified by key factors including age, sex, prior COVID-19 diagnosis, prior vaccination status and whether patients are immunosuppressed. We will estimate the number of events expected among the vaccinated and COVID-19 cohorts using indirect standardisation by age and sex (with 10-year age bands), using the general population cohort as the standard population. We will calculate standardized incidence rate ratios (SIRs) and 95% confidence intervals comparing observed and expected rates. Rates will be reported overall, and by 10-year age bands, by sex, by prior COVID-19 diagnosis, by prior vaccination status and whether patients were immunosuppressed. A standardized incidence rate ratio above 1 will indicate that the observed rate for a specific outcome is higher than what is expected in the general background population.

Table 8: Primary, secondary, and subgroup analysis specification

A. Primary analysis

Hypothesis:	Objective 1 -3: Not applicable, descriptive incidence rate. Objective 4: use of intensive care services during a hospitalisation can be considered as key intermediate events between testing positive for SARS-COV-2 or having a clinical diagnosis of COVID-19 in an outpatient setting on the one end to a COVID-19-related death on the other. Objective 5: Covid-19 infection or vaccination may change the incidence rate of study events in population.
Exposure contrast:	Objective 1 -3: Not applicable, descriptive incidence rate. Objective 4: Not applicable, risk factor analysis Objective 5: Infected or vaccinated vs. the non-infected or non-vaccinated population
Outcome:	Objective 1 -3: Incidence rates of VTE, ATE Objective 4: VTE, ATE, death Objective 5: Incidence rates of VTE, ATE
Analytic software:	R

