In a secondary analysis pulmonary embolism and deep vein thrombosis will be assessed separately. We will also assess portal vein thrombosis, splanchnic venous thrombosis (SVT) and cerebral venous sinus thrombosis separately.

2. Arterial thromboembolic events
In a secondary analysis acute myocardial infarction and acute ischemic stroke will be assessed separately. We also identify stroke in general, for which we will include both ischemic, haemorrhagic and non-specifically recorded stroke.

3. Cardiovascular events
Instances of heart failure, cardiac arrhythmia, and angina will be identified. In addition, major cardiovascular events (MACE) will be identified by heart failure, acute myocardial infarction, or stroke, or the occurrence of sudden cardiac death. As a sensitivity analysis, we will require that events were identified by hospitalisation admission or discharge records.

Table 9 Sensitivity analyses – rationale, strengths and limitations

	What is being varied? How?	Why? (What do you expect to learn?)	Strengths of the sensitivity analysis compared to the primary	Limitations of the sensitivity analysis compared to the primary
Restrict to RT-PCR test	In main analysis, the exposure definition of “Positive test result for SARS-CoV-2” will include all type of test. In the sensitivity analysis, we will restrict to RT-PCR test.	As a result of changes in the availability of population wide RT-PCR and home self-reported lateral flow tests during the Omicron period, it may not be possible to exclusively use RT-PCR tests when identifying positive test results in all datasets.	Increase specificity of exposure definition.	Loss in sensitivity.

	Phase II C3-001 – Study Protocol	
	Author(s): [name], [name]	Version: v3.1
		Dissemination level: public

Require inpatient cardiovascular events only	In the outcome definition of cardiovascular events, restrict to hospitalisation admission or discharge records	Cardiovascular events are acute and usually lead to inpatient admission	Increase specificity of exposure definition.	Loss in sensitivity.

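### Table 1 calls three databases without inpatient data complete for outcome events; their incidence rates risk under-ascertainment, and the COVID-19 SIR would be biased low if capture is poorer after COVID-19 than in background

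*Protocol*

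**What the plan says.** Section 8.2 states which databases serve which objectives. "Records on Covid-19 infection and vaccination (needed for objectives 2 to 5) will be available in all purposed databases except Estonia Biobank", and the Estonian entry in Table 1 reads "Geographic representative (objective 1 only)". Four databases therefore supply the COVID-19 and vaccine SIRs: SIDIAP, CPRD GOLD, IQVIA Germany and IPCI.

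On care setting, section 8.2 says "Inpatient admission and intensive care use (needed for objective 4) will be available in SIDIAP", and the Setting row of Table X in section 7 is explicit: "Inpatient information is only available in SIDIAP". Table 1 lists CPRD GOLD and IPCI as primary care and IQVIA Germany as "outpatient visits of primary care physicians and a sample of specialists". The justification given for each of these three is nevertheless "Complete records on SARS-CoV-2 infection, Covid-19 vaccination, and outcome events of interest (objectives 1 to 5, exclude 4b on worsening covid-19"), so only objective 4b is held back.

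Table 6 lists both inpatient and outpatient settings for every outcome in every cohort. The Table 9 row that restricts cardiovascular outcomes to hospital records is justified by "Cardiovascular events are acute and usually lead to inpatient admission".

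Section 8.8.5 obtains expected events "using indirect standardisation by age and sex (with 10-year age bands), using the general population cohort as the standard population". Section 8.9 pools all databases by random-effects meta-analysis and reports I². Section 11 says that only reliably identifiable cohorts and outcomes will be assessed, that recording is assumed similar over time, and that outcomes will not be validated against case notes.

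**The concern.** The completeness label and the stated absence of inpatient data are compatible only if hospital diagnoses flow back reliably into the primary-care or office record. The protocol does not say that they do. An event first diagnosed in hospital, or fatal there, would otherwise be seen in these three databases only if someone later entered it.

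Two results are exposed. The first is the absolute incidence rates of objectives 1 to 3, which are too low wherever capture is incomplete. The second is the SIR of objective 5, which is affected only if capture differs between the exposed and background cohorts.

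Nothing planned would reveal either problem. The hospital-record analysis in Table 9 raises specificity, covers cardiovascular events only, and can run only where inpatient records exist. Section 11 does not mention missed hospital-diagnosed events, and it gives no criterion for reliable identification. The pooled SIR mixes databases with and without inpatient records, so a gap between SIDIAP and the others could be read as true heterogeneity.

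**Working it through.** The protocol states no outcome sensitivity, capture rate or expected SIR, so there is no planned figure to reproduce.

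**1. How much of the study is affected (Table 1 counts).** Three of the four SIR databases have no inpatient data.
- COVID-19 feasibility counts: 360,198 + 1,723,895 + 941,329 = 3,025,422 of 6,891,398 (43.9%).
- VTE feasibility counts: 219,844 + 392,674 + 57,087 = 669,605 of 771,571 (86.8%).

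**2. Effect on rates and on the SIR.** Let p be the share of events diagnosed in hospital (p0 background, p1 after COVID-19). Let c_in and c_out be the probabilities that an in-hospital or other event reaches the outpatient record. Assuming no false positives:

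- capture in a cohort: S = p·c_in + (1 − p)·c_out
- observed rate = true rate × S
- observed SIR = true SIR × S1/S0

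All inputs below are assumptions: c_out = 0.95, c_in = 0.5, 0.7 or 0.85, and three pairs with p1 above p0.

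| p0, p1 | c_in | S1 | S0 | S1/S0 |
|---|---|---|---|---|
| 0.4, 0.6 | 0.5 | 0.68 | 0.77 | 0.88 |
| 0.4, 0.6 | 0.7 | 0.80 | 0.85 | 0.94 |
| 0.4, 0.6 | 0.85 | 0.89 | 0.91 | 0.98 |
| 0.4, 0.8 | 0.5 | 0.59 | 0.77 | 0.77 |
| 0.4, 0.8 | 0.7 | 0.75 | 0.85 | 0.88 |
| 0.4, 0.8 | 0.85 | 0.87 | 0.91 | 0.96 |
| 0.5, 0.9 | 0.5 | 0.545 | 0.725 | 0.75 |
| 0.5, 0.9 | 0.7 | 0.725 | 0.825 | 0.88 |
| 0.5, 0.9 | 0.85 | 0.86 | 0.90 | 0.96 |

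The SIR loss runs from about 2% to 25%, so a true SIR of 2.0 would appear as about 1.96 down to 1.50. On the same inputs the background rate is understated by 9% (1 − 0.91) to 28% (1 − 0.725), and the COVID-19 rate by 11% (1 − 0.89) to 46% (1 − 0.545).

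**3. When the SIR is not biased low.**
- If p1 = p0 with the same capture probabilities, or if c_in = c_out, then S1 = S0 and the factor is exactly 1, however poor the capture.
- If the in-hospital share is lower after COVID-19, the factor exceeds 1. Swapping the first pair (p0 = 0.6, p1 = 0.4) gives 0.91/0.89 = 1.02 to 0.77/0.68 = 1.13.

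**4. A second mechanism.** The in-hospital share may be equal while re-entry of hospital events differs. With p = 0.8 in both cohorts and c_out = 1, a fall in c_in from 0.8 to 0.6 gives (1 − 0.8×0.4)/(1 − 0.8×0.2) = 0.68/0.84 = 0.81. A rise from 0.6 to 0.8 gives 0.84/0.68 = 1.24.

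Direction and size therefore depend wholly on quantities the protocol does not give.

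**The case against.** The strongest reply is that the SIR is formed within each database against that database's own background cohort, so under-recording lowers observed and expected counts alike. That stands. A reader might infer from the missing inpatient data that the COVID-19 SIR is biased low, or always biased toward a smaller excess. The documents do not support this, because they give no in-hospital share and no capture rate for any cohort. In the three databases the COVID-19 cohort is essentially cohort 2, which Table 2 indexes in outpatient care, and section 6 notes that Omicron may run a milder course. A large shift of events into hospital is plausible but unproven.

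Two further readings go too far. The Table 9 sentence concerns cardiovascular events. MI and stroke enter through MACE, but PE and DVT are not named, so it cannot be quoted for VTE. A reader might also infer that the plan's infection-versus-vaccination estimate is compressed. No such estimate is planned, since objective 5 compares each exposed cohort with background.

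Table 1 also gives VTE counts per active subject of 1.76% in SIDIAP (101,966/5.8M), against 7.33% in CPRD GOLD, 4.62% in IQVIA Germany and 4.11% in IPCI. These are undated counts and not rates, and they say nothing about differences between cohorts, but they show no sign of gross under-capture.

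Finally, incidence is reported by database, I² is reported, and section 11 promises to detail each partner's data elements. This helps, but it neither withdraws the completeness claim nor names the possible loss.

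**Conclusion.** The contradiction holds. Three databases are called complete for outcome events although the protocol says that inpatient information exists only in SIDIAP, and for cardiovascular events its own Table 9 says admission is usual. Incidence rates in these databases are at risk of understatement.

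The effect on the COVID-19 SIR is conditional. There is none if capture is equal in the COVID-19 and 2017-2019 cohorts, and the SIR is biased low if capture is poorer after COVID-19. The 2% to 25% loss rests on assumed in-hospital shares that are higher after COVID-19 (0.6 to 0.9 against 0.4 to 0.5) and on assumed capture probabilities. It illustrates the possible size and is not an estimate. The point merits a change because the plan cannot at present tell these situations apart, and one of its databases could help to do so.

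**What to change.** 1. **Table 9:** add a SIDIAP sensitivity analysis that recomputes the rates and the COVID-19 and vaccine SIRs with hospital-sourced outcome records masked in both the background and the exposed cohorts. Report the ratio of the masked to the full-data SIR as an indication of size and direction. State that it reflects recording in SIDIAP and may not transfer to the UK, Germany or the Netherlands.
2. **Section 8.9:** show the SIDIAP SIR separately, beside the pooled SIR and the SIR from the databases without inpatient data. SIDIAP need not become the main result, since that would rest the conclusion on one country because of a bias not yet measured.
3. **Table 1 and section 11:** for CPRD GOLD, IQVIA Germany and IPCI, replace the claim of complete outcome records with a statement that only events recorded in primary or outpatient care are captured. Add the limitation in conditional form: rates may be understated, and the COVID-19 SIR would be biased low if hospital-diagnosed events are captured less often after COVID-19 than in background.

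The cost is one extra run in one database and some rewording, with no new data. The downside is a less favourable description of three databases.
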